**AMENDMENT HISTORY**

SAP Version	Issue Date
Original SAP	August 24, 2020
Amendment 1	February 4, 2021
Amendment 2	February 18, 2021

Amendments below are listed beginning with the most recent amendment.

**Amendment 2**

Applicable Section(s)	Description of Change (s)
Section 2.3. Definition of Subgroups	The subgroup “Staining intensity (central)” was added.
Section 8. BIOMARKER	The end-of-treatment of scheduled time point was added. This change was added to clarify the time point for biomarkers.

**Amendment 1**

Applicable Section(s)	Description of Change (s)
Section 2.2. Analysis Set	A note was added in the description of response evaluable population: confirmed evaluable by an independent central radiology review means the participant had at least one target lesion confirmed by ICRR. This note was added to clarify the meaning of “evaluable” and avoid confusion.
Section 3. INTERIM AND FINAL ANALYSIS	The original description "At the interim and final analysis, all analysis planned in this SAP will be performed" was changed. At the interim analysis, only selected analyses will be performed. Also, a table of the planned analyses at the interim analysis was added. This change was made as it was a decision from the study team that the results of IA would not be used for New Drug Application considering the expected timing of final analysis and only selected analyses will be performed.
Section 6.2. Adverse Events of Special Interest	The category “hypothyroidism” was deleted from AESI. This change was made as a concordance with the most updated SMQ file.
Section 6.3. Adverse Events of Clinical Interest	The two categories “diabetes and cognitive deficits” were added into AECL. This change was made as a concordance with the most updated SMQ file.
Section 8. BIOMARKER	A new Section 8 was added. Added detailing description of the conduct of Biomarker analyses.

**ABBREVIATIONS**

AE	adverse event
ATC	anatomic and therapeutic Class
CBR	Clinical benefit rate
CI	confidence interval
CRF	case report form
CSR	Clinical Study Report
CTCAE	Common Terminology Criteria for Adverse Events
CV	coefficient of variation
DCR	Disease control rate
DOR	Duration of response
ECOG	Eastern Cooperative Oncology Group
FA	Final Analysis

IA	Interim Analysis
ICRR	Independent Central Radiology Review
IQ	interquartile
MedDRA	Medical Dictionary for Regulatory Activities
ORR	Overall response rate
OS	Overall survival
PFS	Progression free survival
PK	pharmacokinetic(s)
PSA	prostate-specific antigen
SAP	Statistical Analysis Plan
SD	standard deviation
TEAE	treatment-emergent adverse event
TTR	Time to response
WHO	World Health Organization

## **1. INTRODUCTION**

This statistical analysis plan (SAP) contains definitions of analysis sets, derived variables, and statistical methods for all planned analyses for the clinical study report (CSR) for study 56021927SGT2001.

This SAP does not include planned analyses on pharmacogenomics data.

The term “study intervention” throughout the SAP, refers to study drug.

### **1.1. Trial Objectives**

#### **Primary Objectives**

To evaluate the overall response rate (ORR) of apalutamide in combination with a GnRH agonist in participants with AR expressing locally advanced or recurrent/metastatic SGC.

#### **Secondary Objectives**

To evaluate the efficacy, pharmacokinetics (PK), and safety endpoints or parameters with apalutamide plus a GnRH agonist in participants with AR expressing locally advanced or recurrent/metastatic SGC.

### **1.2. Trial Design**

This is an open-label, single-arm, multicenter, Phase 2 study to evaluate the efficacy and safety of apalutamide in combination with a GnRH agonist in participants with AR expressing locally advanced or recurrent/metastatic SGC.

The study will consist of a screening phase, a treatment phase, and a follow-up phase. Study intervention will continue until disease progression, unacceptable toxicity, death, or the end of the study. Study intervention will be discontinued if a participant meets any of criteria for discontinuation of study intervention. Dose modifications will be made as required according to dose modification rules. An independent central radiology review (ICRR) will be used to reduce potential bias during data collection and evaluation of the primary endpoint of overall response and secondary endpoints including progression-free survival (PFS).

An interim analysis will be performed when 12 response evaluable participants are observed for at least 24 weeks after the initiation of study intervention. Final analysis will be conducted when 24 response evaluable participants are observed for at least 24 weeks.

### **1.3. Statistical Hypotheses for Trial Objectives**

The primary hypothesis of this study is that apalutamide in combination with a GnRH agonist will demonstrate significant antitumor activity in participants with AR expressing locally advanced or recurrent/metastatic SGC.

## 1.4. Sample Size Justification

In this study, ORR of 40% is assumed (Fushimi 2018). Under the alternative hypothesis for ORR of 40%, using an O'Brien-Fleming boundary based on Lan-DeMets' alpha spending function (Jennison 1999), to achieve at least 80% power for rejecting the null hypothesis for ORR of 14% by exact test based on the binomial distribution while maintaining overall 1-sided Type-1 error below 2.5%, at least 24 evaluable participants will be required. The null hypothesis of ORR of 14% for the threshold value is an estimate based on published data (Viscuse 2019).

An ORR will be tested using exact test based on the binomial distribution, and the null hypothesis for ORR of 14% will be rejected and efficacy will be declared if statistical significance is observed using an O'Brien-Fleming boundary based on Lan-DeMets' alpha spending function as described in Section 3. Futility analysis is also used in this study. Details are described in Section 3. With 24 evaluable participants and 1 interim analysis based on the boundaries, overall Type-1 error will be lower than the one-sided significance level of 2.5% and power will be higher than 80%. The lower limit of 2-sided 95% Clopper-Pearson confidence interval (CI) for ORR will exceed the threshold value of 14% if efficacy is declared based on the boundaries in Table 1.

## 1.5. Randomization and Blinding

Not applicable.

## 2. GENERAL ANALYSIS DEFINITIONS

**Study Day:** For both efficacy and safety, study day will be calculated in reference to the date of first dose. Study Day 1 corresponds to the date the subject receives first dose of study intervention. All efficacy and safety assessment at all visits will be assigned a day relative to the date of Study Day 1.

**Cycle:** For the purpose of the study, a treatment cycle is defined as 28 days. Subjects will begin taking study intervention on Day 1 of Cycle 1.

**Baseline Value:** Unless otherwise specified, the baseline value will be defined as the closest measurement prior to the first dose of study intervention. Change from baseline will be defined as (postbaseline value – baseline value).

**Treatment Duration:** Treatment duration will be defined as the duration of time from the date of the first dose of study intervention to the date of last dose of study intervention.

**Time to event:** Time to event calculations will be defined as the time from Study Day 1 to the date of the event of interest. Time to event or duration of event endpoints will be based on the actual date of the event, not visit number or visit label.

### 2.1. Visit Windows

The Treatment Phase will begin at Cycle 1 Day 1 of treatment and will continue until study intervention is discontinued. Visits for each cycle will have a  $\pm 2$  day window.

Subjects' time on study will be determined in Study Days. Study Day 1 will be defined as the first day of dosing. Positive study days will count forward from Study Day 1. Study Day -1 will be the day before Study Day 1, and all subsequent negative study days will be measured backward from Study Day -1. There will be no Study Day 0. The last available value collected prior to the first dose of study intervention will be used as the baseline value.

## 2.2. Analysis Set

For purposes of analysis, the following populations are defined:

Population	Description
Enrolled	All participants who sign the ICF.
Treated	All participants who receive at least 1 dose of study intervention. This population will be used for all analyses including efficacy, safety, and biomarker unless otherwise specified.
Response evaluable	All participants who are AR positive by local test and who are confirmed evaluable by an independent central radiology review (ICRR). Also, all participants who receive at least 1 dose of study intervention and who have at least 1 postbaseline disease assessment or died due to disease progression before the first postbaseline disease assessment. This population will be considered for primary efficacy analysis.  Note: Confirmed evaluable by an independent central radiology review means the participant had at least one target lesion confirmed by ICRR.
Pharmacokinetic	All participants with at least 1 apalutamide and/or N-desmethyl apalutamide concentration data after the first study intervention administration.

## 2.3. Definition of Subgroups

Subgroup	Definition
CCI	
Gender	
 
Female
 
Male
 

Prior lines of systemic therapy	
 
0
 
<math>\geq 1</math>
 

ECOG performance status at baseline	
 
<math>\leq 1</math>
 
<math>\geq 2</math>
 

Disease status	
 
Locally Advanced
 
Recurrent/Metastatic
 

Histology Classification (central)	
 
Salivary Duct Carcinoma
 
Other (Non Salivary Duct Carcinoma)
 

Subgroup	Definition
CCI	

Subgroup analysis will be performed for all efficacy endpoints as exploratory analysis if there are sufficient subjects. Details for safety endpoints to be done will be listed in Section 6.1.

#### 2.4. Imputation Rules for Missing AE Date/Time of Onset/Resolution

Treatment-emergent adverse events (TEAEs) for the treatment phase are those events with an onset date/time on or after the start of study intervention through the day of last dose plus 30 days is considered to be treatment -emergent.

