8.2.4. Clinical Safety Laboratory Assessments

Blood samples for serum chemistry and hematology will be collected as noted in Section 10.2, Appendix 2, Clinical Laboratory Tests. Required laboratory tests must be performed as per SoA (Section 1.3). The investigator must review the laboratory results, document this review, and

record any clinically relevant changes occurring during the study in the Adverse Event section of the eCRF. For example, laboratory abnormalities leading to an action regarding study intervention (dose change, temporary stop, delay of the start of a cycle, or permanent stop) or the start of concomitant therapy should be reported. For each laboratory abnormality which is also reported as an AE, the following laboratory values should be reported in the laboratory section of the eCRF: the value indicative of the onset of each toxicity grade, the most abnormal value observed during the AE, and the value supporting recovery to Grade ≤ 1 or to baseline values.

In the event of additional safety monitoring, unscheduled laboratory assessments may be performed as required. Some laboratory assessments collected during the posttreatment phase of this study, may be delegated to a home health provider.

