9.4.3. Safety Analyses

All safety analyses will be made on the treated population.

Adverse Events

The verbatim terms used in the eCRF by investigators to identify AEs will be coded using the Medical Dictionary for Regulatory Activities (MedDRA). Toxicities will be graded for severity according to NCI-CTCAE, version 5.0. Any AE occurring at or after the initial administration of study intervention through the day of last dose plus 30 days is considered to be treatment-emergent. All reported AEs will be included in the analysis. For each AE, the percentage of participants who experience at least 1 occurrence of the given event will be summarized.

Clinical Laboratory Tests

Laboratory data will be summarized by type of laboratory test. Descriptive statistics will be calculated for all laboratory analyte at baseline and at selected scheduled timepoints. Parameters with predefined NCI-CTCAE toxicity grades will be summarized. Change from baseline to the worst toxicity grade experienced by the participants during the study will be provided as shift tables.

Vital Signs

Descriptive statistics of blood pressure (systolic and diastolic) values and changes from baseline will be summarized.

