The sponsor reserves the right to close the study site or terminate the study at any time for any reason at the sole discretion of the sponsor. Study sites will be closed upon study completion. A

study site is considered closed when all required documents and study supplies have been collected and a study-site closure visit has been performed.

The investigator may initiate study-site closure at any time, provided there is reasonable cause and sufficient notice is given in advance of the intended termination.

Reasons for the early closure of a study site by the sponsor or investigator may include but are not limited to:

- Failure of the investigator to comply with the protocol, the requirements of the IEC/IRB or local health authorities, the sponsor's procedures, or GCP guidelines
- Inadequate recruitment of participants by the investigator
- Discontinuation of further study intervention development

10.4. Appendix 4: Adverse Events: Definitions and Procedures for Recording, Evaluating, Follow-up, and Reporting

ADVERSE EVENT DEFINITIONS AND CLASSIFICATIONS

Adverse Event

An adverse event is any untoward medical occurrence in a clinical study participant administered a medicinal (investigational or non-investigational) product. An adverse event does not necessarily have a causal relationship with the intervention. An adverse event can therefore be any unfavorable and unintended sign (including an abnormal finding), symptom, or disease temporally associated with the use of a medicinal (investigational or non-investigational) product, whether or not related to that medicinal (investigational or non-investigational) product. (Definition per International Conference on Harmonisation [ICH])

This includes any occurrence that is new in onset or aggravated in severity or frequency from the baseline condition, or abnormal results of diagnostic procedures, including laboratory test abnormalities.

Note: The sponsor collects AEs starting with the signing of the ICF (refer to All Adverse Events under Section 8.3.1, Time Period and Frequency for Collecting Adverse Events and Serious Adverse Events Information, for time of last adverse event recording).

Serious Adverse Event

An SAE based on ICH and EU Guidelines on Pharmacovigilance for Medicinal Products for Human Use is any untoward medical occurrence that at any dose:

- Results in death
- Is life-threatening

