### **6.1. Adverse Events**

The verbatim terms used in the CRF by investigators to identify adverse events (AE) will be coded using the Medical Dictionary for Regulatory Activities (MedDRA). Any AE occurring at or after the initial administration of study agent through the day of last dose plus 30 days is considered to be treatment emergent. If the event occurs on the day of the initial administration of study agent, and either event time or time of administration are missing, then the event will be assumed to be treatment emergent. If the event date is recorded as partial or completely missing, then the event will be considered to be treatment emergent unless it is known to be prior to the first administration of study agent based on partial onset date or resolution date. All reported treatment-emergent adverse events will be included in the analysis. For each adverse event, the number and percentage of subjects who experience at least 1 occurrence of the given event will be summarized.

A summary for tables and listings is shown in [Table 7](#):

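### Treatment-emergent status is set by onset date with no worsening rule, so an AE that begins before first dose and worsens on study drug can be missing from the TEAE tables, depending on how sites record it

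*SAP*

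**What the plan says.** Three places define treatment-emergent, and all three use timing alone.

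- SAP 2.4: TEAEs "are those events with an onset date/time on or after the start of study intervention through the day of last dose plus 30 days".
- SAP 6.1: "Any AE occurring at or after the initial administration of study agent through the day of last dose plus 30 days".
- Protocol 9.4.3: "Any AE occurring at or after the initial administration of study intervention through the day of last dose plus 30 days".

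The two documents differ on what is then analysed. SAP 6.1 has "All reported treatment-emergent adverse events will be included in the analysis"; Protocol 9.4.3 has "All reported AEs will be included in the analysis".

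The AE definition in Protocol 10.4 (Appendix 4) is wider than onset: "This includes any occurrence that is new in onset or aggravated in severity or frequency from the baseline condition". On grade changes within an event, the relevant text is Protocol 8.2.4. For a laboratory abnormality that is also an AE, it asks the site to enter in the laboratory section of the eCRF "the value indicative of the onset of each toxicity grade, the most abnormal value observed during the AE", plus the value that supports recovery.

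**The concern.** A TEAE definition usually has two limbs: new events, and existing events that get worse on treatment. Only the first is written here. A participant may develop, say, a grade 1 event after consent that becomes grade 3 or serious on apalutamide plus goserelin. If it is still held as one record, its onset precedes first dose and the classification rule excludes it.

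An onset-only rule can leave on-treatment worsening out but can never add any, so the error runs towards understating toxicity. The study treats only about 24 people, and Protocol 2.2 says that apalutamide's safety in women has not been studied. A single event can therefore visibly change a reported rate. Outputs could also disagree. SAP 4.2 tabulates reasons for stopping treatment whatever the AE onset, so a participant who stops for a worsened screening AE could appear there and not in the TEAE discontinuation table.

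**Working it through.** The plan gives no figure for this point, so the check is a comparison of texts followed by a scale calculation.

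**1. Is there a worsening clause anywhere?** No. SAP 2.4 tests onset date and time. SAP 6.1 and Protocol 9.4.3 test when the event occurs. The missing-date rule in SAP 6.1 has the same logic: an event with an incomplete date is treated as emergent unless it is known to precede first dose. A known pre-dose onset therefore settles the classification, whatever happens later.

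**2. Can such events arise?** Yes. Protocol 8.3.1 collects AEs from signed consent. Protocol 5 places screening within the 28 days before first dose. The note at the end of Protocol 5.2 foresees a change in clinical status after screening and before dosing, and allows supportive treatment in that interval. Protocol 8.2.4 asks for laboratory abnormalities that prompt concomitant therapy to be reported.

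**3. What happens to one that worsens on drug?** There are two routes.

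- A new AE record dated at the worsening. Its onset lies inside the window, so it is a TEAE.
- A higher grade on the original record. Its onset stays before first dose, so it is not a TEAE.

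Appendix 4 makes the first route possible, because aggravation from baseline is within the AE definition, but it does not require a new record. Protocol 8.2.4 fits the second route, because it speaks of several grades during one AE, but it governs which laboratory values are entered, not the AE record or its onset date. Neither document settles the matter.

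**4. Which outputs would miss the event on the second route?** In SAP Table 7 the rows for TEAEs, serious TEAEs, grade 3 or higher TEAEs, and TEAEs leading to discontinuation, death, dose reduction or interruption are all labelled TEAE. So are the drug-related tables and the time-period table. Nearly all the safety rows for the interim analysis in SAP Table 2 carry the same label.

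**5. Which outputs might still show it?**

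- The special-interest and clinical-interest rows of Table 7 are not labelled TEAE, although Table 2 does label special-interest events TEAE at the interim.
- The death summary in SAP 6.4 is by time period and cause, without a TEAE restriction.
- SAP 6.5 has shift tables to worst grade for selected laboratory parameters, and liver summaries and listings.

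**6. Scale.** SAP 6.1 counts participants with at least one occurrence, and the target number treated is 24 (Protocol 4.1). If k participants have an omitted event and no other qualifying event in the same row, the row falls by k/24:

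- k = 1: 1/24 = 4.2 percentage points
- k = 2: 2/24 = 8.3 percentage points
- k = 3: 3/24 = 12.5 percentage points

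The documents give no value for k. A participant who has another event in that row causes no change.

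**The case against.** The strongest reply is that the AE definition already covers the case. Aggravation from baseline is an AE, and SAP 2 sets baseline at the last measurement before first dose. On-drug worsening can thus be an event in its own right, dated within the window. This stands as a possible reading, and it is why omission is conditional and not certain. It does not close the gap, because no text tells sites to open a new record, so TEAE counts would depend on site practice.

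A second reply is that few events are exposed. Screening examination findings and clinically significant screening ECG findings go to medical history (Protocol 8.2.1 and 8.2.3), and significant post-baseline examination changes are recorded as AEs. What remains is an event that arises after consent, persists to first dose, worsens on treatment and is kept on its old record. This also stands, and it limits the size.

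A reader might infer two stronger things. One is that these events vanish from every AE table; step 5 of the working lists outputs that are not tied to TEAE status, and SAP 6.1 also lists female safety records without stating that limit. The other is that Protocol 8.2.4 fixes a single onset for each laboratory AE. It does not: it refers to an onset for each grade, concerns laboratory values only, and says nothing of non-laboratory events.

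**Conclusion.** The point holds in conditional form. The written rule has no limb for worsening, and it excludes any AE record with a known pre-dose onset from the TEAE tables even if the event becomes severe, serious or treatment-limiting on study drug. Whether that happens depends on a recording practice that the documents leave open. The mismatch between SAP 6.1 and Protocol 9.4.3 on which AEs are analysed does not depend on that practice and needs to be reconciled in any case.

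The effect cannot be estimated. It is probably small in number, and each participant counts for 4.2 percentage points in a row, assuming 24 treated and no other qualifying event for that participant. The direction is towards understatement. The primary endpoint is unaffected. The change is worth making because it is cheap and removes the dependence on site practice.

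**What to change.** In SAP 2.4 and 6.1:

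- Keep the present onset limb. Add that an AE present before first dose is treatment-emergent if its toxicity grade or seriousness increases from first dose through last dose plus 30 days.
- Use the date of the first increase as the analysis onset date, including in the time-period table.
- Where a site has opened a new record for the worsening, count it once.
- Where the date of increase is missing, treat a pre-dose AE as treatment-emergent if its worst recorded grade exceeds its pre-dose grade.
- Align SAP 6.1 with Protocol 9.4.3 on whether all AEs or only TEAEs are analysed.

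The cost is a few sentences in the SAP and some derivation work. For laboratory AEs, Protocol 8.2.4 already asks for the values that mark each grade. For other AEs the rule needs grade-change dates, and the documents do not confirm that the eCRF captures them. The fallback needs both the pre-dose grade and the worst grade to be kept, so the sponsor should check the AE form and its completion guidelines before finalising the wording.
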